#### BP systolic >160 mmHg, or diastolic >100 mmHg:

Re-assessment: Participants who develop significant hypertension with systolic blood pressure (BP) averages of three measurements of ≥ 160 mm Hg, and/or diastolic BP of ≥ 100 mm Hg, but less than 180/110 mmHg, will be re-assessed on 2 separate occasions.

They should be re-counselled as to the foods and drink to be avoided with study treatment, as non-compliance to this could be an important aspect to the hypertension.

- If this evaluation supports the conclusion of a significant increase in blood pressure, the investigator will assess potential causes. If the increase is determined to be associated with study treatment, a de-challenge/re-challenge will be performed: participants will discontinue DZD. If, after ≥ 10 h (> 5 x t1/2 of DZD) after the last dose, BP has dropped significantly, a re-challenge with daily BP measurements will be considered.
- Treatment with BDQ, DLM and MXF should continue throughout.
- Continued hypertension after re-assessment: participants who develop persistent hypertension ≥ 160/100 mmHg after evaluation and adequate antihypertensive treatment, including those who have undergone a re-challenge with DZD, will discontinue all study treatment and complete TB treatment according to national TB program guidelines. These participants will receive follow-up to determine whether the condition normalizes after discontinuation of study treatment.

#### BP systolic >180 mmHg, or diastolic >110 mmHg:

- Immediate stop: Participants who develop hypertension with systolic blood pressure (BP) averages of three measurements of ≥ 180 mm Hg, and/or diastolic BP of ≥ 110, will stop study treatments immediately, and receive antihypertensive treatment. During follow-up, investigators should attempt to determine whether the condition normalizes after discontinuation of study treatment, in order to better judge relatedness to IMP.
- Pregnancy stopping criterion: a female patient will stop treatment immediately, if a pregnancy test is positive at any time. Further management is described under Chap. 14.11..
- Serotonin syndrome stopping criterion: A patient will stop treatment with DZD if at least one of the following criteria are fulfilled, which are indicative of serotonin syndrome (Hunter Serotonin Toxicity Criteria):
  - Spontaneous clonus
  - Inducible clonus PLUS agitation or diaphoresis
  - Ocular clonus PLUS agitation or diaphoresis
  - o Tremor PLUS hyperreflexia
  - Hypertonia PLUS temperature above 38°C PLUS ocular clonus or inducible clonus
- Convulsions/seizures stopping criterion: A patient will stop study treatment if clinically significant convulsions are observed in the discretion of the investigator.

In such a case, the following examinations should be done as soon as possible, after stabilisation of the participant' s condition, to assess the aetiology and contributing factors to the event in order to assess relatedness to study drugs.

- Clinical assessment: ventilation pattern, neurological abnormalities, body temperature, blood pressure, heart rate
- Quick bed-side test: glucose
- o ECG
- Question on concomitant medications, including herbal or over-the-counter preparations
- Question on alcohol or other drug intake, regular abuse and changes in pattern of use that might have led to a withdrawal
- Re- question on own and family history of seizures (to be done at screening, but repeated in this case)
- Draw safety blood sample, including all safety blood tests that are done as per schedule of events

#### PLUS:

Malaria microscopy and rapid test, if in a malaria endemic area; to exclude cerebral malaria

- Cerebral imaging like computed tomography (CT) or magnetic resonance imaging (MRI) are indicated; to be conducted urgently if cerebral haemorrhage is suspected as the underlying cause. It is to be noted that CT is suboptimally sensitive to describe a stroke during the first 24h but is highly sensitive to describe haemorrhage.
- Electroencephalography (EEG) should be conducted when patient is stable.

In addition, a seizure can be a symptom of CNS infection such as meningitis or encephalitis. If this is suspected, a lumbar puncture may be seen to be in the patient' s best interest, after elevated intracranial pressure has been duly excluded by ophthalmoscopy or cerebral imaging.

The information obtained by these diagnostics will be transmitted to the sponsor medical expert on the immediately reportable event form within 24h, and any updates transmitted and discussed in a timely manner.

# 14 REPORTING ADVERSE EVENTS

#### 14.1 Definitions

For safety monitoring and reporting purposes, a drug related AE is defined as an adverse event that is judged to be definitely, probably or possibly related to (one of) the study drug(s). Adverse events will be graded for severity according to the CTCAE 5.0 grading system.

• Proportion of adverse events of Grade 3 or Grade 4 severity

- Proportion of adverse events possibly, probably or definitely related to study drugs.
- Proportion of treatment discontinuations or interruptions related to adverse events
- Specific ECG endpoints:
  - Frequency, severity and type of ECG alterations
  - Changes to PR, RR, QRS, QT, Fridericia-corrected QT [QTcF]
  - Proportion of participants with QTcF > 500ms on treatment
  - Proportion of participants who experience a prolongation of QTcF > grade 3

Term	Definition		
Adverse Event (AE)	Any untoward medical occurrence in a patient or clinical trial subject to whom a medicinal product has been administered including occurrences which are not necessarily caused by or related to that product.		
Adverse Reaction (AR)	Any untoward and unintended response to an investigational medicinal product related to any dose administered.		
Unexpected Adverse Reaction (UAR)	An adverse reaction, the nature or severity of which is not consistent with the information about the medicinal product in question set out in the summary of product characteristics (or Investigator brochure) for that product.		
Serious Adverse Event (SAE) or Serious Adverse Reaction (SAR) or Suspected Unexpected Serious Adverse Reaction (SUSAR)	
 
Respectively any adverse event, adverse reaction or unexpected adverse reaction that:
 
results in death
 
is life-threatening*
 
requires hospitalisation or prolongation of existing hospitalisation**
 
results in persistent or significant disability or incapacity
 
consists of a congenital anomaly or birth defect
 
is medically significant***
 
		

\*The term 'life-threatening' in the definition of 'serious' refers to an event in which the patient was at risk of death at the time of the event; it does not refer to an event which hypothetically might have caused death if it were more severe.

\*\*Hospitalisation is defined as an inpatient admission, regardless of length of stay, even if the hospitalisation is a precautionary measure for continued observation. Hospitalisations for a preexisting condition (including elective procedures that have not worsened) do not constitute an SAE. Due to the seriousness of the disease in this study, some patients may be admitted to hospital for the initial Phase of their trial treatment. This would not qualify as an SAE, although if that hospitalisation had to be prolonged beyond the normal length of admission, then it would be an SAE.

\*\*\*A medically serious event is one which does not fit the other outcomes, but the event may jeopardize the patient and may require medical or surgical intervention (treatment) to prevent one of the other outcomes. An example might include allergic bronchospasm, haemoptysis, or seizure requiring treatment in an emergency room, that do not result in hospitalization.

## 14.2 Clarifications and exceptions

Occurrences will be registered as AE from administration of the first dose of study drugs. All events that occur or are elicited before administering any study drugs, e.g. screening laboratory abnormalities qualifying as Adverse Events, will be recorded as medical history. If such events meet criteria for seriousness, they will nevertheless be reported as SAEs.

Abnormalities which are not clinically significant as per the qualified judgement of the investigator do not constitute adverse events and are not recorded and reported as such. However, these abnormalities may be analysed and reported in the study report.

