# 9 TRIAL ENDPOINTS

#### 9.1 Primary Endpoints

#### 9.1.1 Primary Safety endpoint

Participants will be regularly assessed for AEs during treatment and follow-up phase, including assessments of vital signs, physical examination, weight, detailed neurological examination, colour vision and visual acuity tests, 12-lead ECGs and routine clinical laboratory tests (including chemistry, haematology and urinalysis data).

The safety of DZD will be investigated by evaluation of:

• Proportion of patients experiencing expected oxazolidinone class toxicities, defined as peripheral or optical neuropathy, or incident leukopenia, anemia or thrombocytopenia, or adverse events in line with tyramine pressor response, all of Grade 2 or higher, possibly, probably or definitely related to DZD

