# **13.6 Methods of avoiding bias**

This study will be open-label, patients and physicians will be aware of treatment allocation. To ensure unbiased assessment of efficacy endpoints, the personnel assessing patients' outcomes, like the microbiology laboratory staff or the sponsor medical expert discussing the possibility of recurrent disease, will remain blinded to treatment assignment throughout the whole study. Every effort will be made to maintain this blinding.

Further, there will not be any cumulative summary of study data by randomized treatment arms generated, except for data to be provided to the independent data safety monitoring board (DSMB) by the unblinded statistician. Such analysis may not be distributed outside of the DSMB.

Determination of MICs for the experimental treatment allocated to the patients will only be made after all other assessments of patient samples have been completed in the respective laboratory or will be done at a different specialised laboratory.

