## 14.10 Clinical Laboratory adverse events

Changes in the results of the clinical laboratory assessment, which the Investigator feels are clinically significant, will be reported as adverse events. It is the Investigators' responsibility to review the results of all laboratory tests as they become available. This review must be documented by the Investigators' dated signature on the laboratory report.

For each abnormal laboratory test result, the Investigator needs to ascertain if this is a clinically significant change from baseline for that individual patient. This determination, however, does not necessarily need to be made the first time an abnormal value is observed. The Investigator may repeat the laboratory test or request additional tests to verify the results of the original laboratory tests.

If this laboratory value is determined by the Investigator to be a negative, clinically significant change from baseline for that patient, it is an adverse event.

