Table 3.2.18 Summary of Group Mean Platelet Count Changes over time

{Similar shell table as Table 3.2.1}

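### The blood-count part of the primary safety endpoint rests on two judgements by an investigator who knows the arm, and no graded, count-based analysis is planned beside it

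*Protocol*

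**What the plan says.** **Endpoint.** Protocol 9.1.1 and SAP 5.1.1 count participants with expected class toxicities. Among these are "incident leukopenia, anemia or thrombocytopenia", and the qualifier on the whole list is "all of Grade 2 or higher, possibly, probably or definitely related to DZD".

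**When a laboratory value becomes an adverse event.** Protocol 14.2: "Abnormalities which are not clinically significant as per the qualified judgement of the investigator do not constitute adverse events and are not recorded" as such. Its next sentence allows such abnormalities to be analysed and reported, but does not require it. Protocol 14.10 applies the same test to laboratory results. If the value is "determined by the Investigator to be a negative, clinically significant change from baseline for that patient, it is an adverse event". No numeric threshold is attached.

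**Who judges.** Protocol 14.5 has the investigator rate causality for each AE. Protocol 13.6: "This study will be open-label, patients and physicians will be aware of treatment allocation". The blinded assessment described there is for efficacy endpoints.

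**Planned laboratory outputs.** Protocol 15.3.3 and SAP 13.2 tabulate participants who worsen from baseline on any variable, laboratory parameters included. The SAP appendix has group-mean shells for platelets (Table 3.2.17) and, under the haemoglobin heading, "Table 3.2.18 Summary of Group Mean Platelet Count Changes over time". There is no leukocyte shell.

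**The concern.** The three cytopenias are defined by laboratory values that every arm provides on the same schedule. As the plan stands, a count that would grade 2 or higher can still stay out of the endpoint if the investigator does not regard it as clinically significant, or does not regard it as related to delpazolid. That investigator knows the dose.

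The trial exists to choose a dose with acceptable safety (Protocol 8.1), and Protocol 4.2 names suppression of haematopoiesis among the main severe class toxicities. If the readiness to record or attribute low counts differs between doses, the dose comparison of the primary safety endpoint carries that difference. Nothing planned would show whether this had happened.

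**Working it through.** The plan states no rate, alpha or power for the safety endpoint, so there is no figure to reproduce. The check follows a low count to the endpoint, then looks at what else is planned, then at size.

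**1. From count to endpoint**

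| Step | Decided by | Source |
|---|---|---|
| Low count becomes a recorded AE | Investigator, on clinical significance | Protocol 14.2, 14.10 |
| Graded by CTCAE 5.0 | Applied to AEs | Protocol 14.1, 14.6 |
| At least possibly related to delpazolid | Investigator, for each AE | Protocol 14.5 |
| Enters the endpoint | Needs all of the above | Protocol 9.1.1, SAP 5.1.1 |

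A count never recorded as an AE has no relatedness rating and so cannot meet the endpoint. An Arm 1 count cannot properly meet it either, because that arm takes 0 mg (Protocol 12.2).

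**2. Data already collected.** A complete blood count with differential and platelets (Protocol 11.3) is due at weeks 1 to 9, 11, 13 and 16, which is 9 + 3 = 12 visits. Screening and week 18 bring this to 14 per participant, with no restriction by arm.

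**3. What the planned outputs give**

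| Output | Per participant? | Graded? | Tied to endpoint? |
|---|---|---|---|
| Worsening from baseline (Protocol 15.3.3, SAP 13.2) | Yes | No | No |
| Abnormalities not called AEs (Protocol 14.2) | Optional | Not stated | No |
| Haematology shells (SAP appendix 3.2) | No, group means | No | No |

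**4. Size.** With 15 per arm, one case is 1/15 = 6.7 percentage points.

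The documents give neither a cytopenia risk r nor the share s of Grade 2 or higher cytopenias that would be recorded and rated related. Both are assumed below. Expected cases in an arm are 15 × r × s; the chance of at least one is 1 − (1 − rs)^15.

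| r | s = 1 | s = 0.5 | s = 0.25 |
|---|---|---|---|
| 10% | 1.5 cases; 79% | 0.75; 54% | 0.38; 32% |
| 20% | 3.0; 97% | 1.5; 79% | 0.75; 54% |
| 30% | 4.5; 99.5% | 2.25; 91% | 1.12; 69% |

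Unequal s between two delpazolid arms can act either way:
- Same true risk of 20%, s = 1 against s = 0.5: 3.0 against 1.5 expected cases, an apparent 10-point difference where there is none.
- True risks of 10% (s = 1) and 20% (s = 0.5): 15 × 0.10 × 1 = 15 × 0.20 × 0.5 = 1.5 each, so a true 10-point difference disappears.

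Relatedness acts separately. If every arm had the same 20% risk and every case on delpazolid were rated at least possibly related, each delpazolid arm would expect 3.0 cases and Arm 1 none.

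**5. Can group means stand in?** Suppose 2 of 15 participants lose 3 g/dL of haemoglobin: the arm mean moves by 2 × 3/15 = 0.40 g/dL. For an assumed SD of 1.0, 1.5 or 2.0 g/dL the standard error, SD/√15, is 0.26, 0.39 or 0.52, so the shift is 1.55, 1.03 or 0.77 standard errors. These inputs are assumptions. Whatever their values, a mean does not show how many participants crossed a grade.

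**The case against.** **There is a laboratory check.** A reader might infer that the SAP has none, or that haematology is shown only as group means. The documents do not support that. SAP 13.2 and Protocol 15.3.3 plan a participant-level tabulation of worsening that does not depend on AE status. This objection stands against the stronger reading. What remains is that the tabulation carries no grade or threshold and no link to the endpoint.

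**The cytopenias may be meant as laboratory findings.** In Protocol 9.1.1 the words for adverse events attach to the pressor component; the cytopenias are named as conditions. The relatedness requirement makes that reading hard to sustain, since causality is rated per AE. If it were intended, the SAP would still need to say how counts are graded and how an unrecorded count gets a relatedness rating.

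**Tolerance of low counts in Arm 1 would bias the comparison.** This too may be inferred, but the relatedness condition already keeps Arm 1 cases out, whether recorded or not. The clinical-significance judgement matters mainly among the four delpazolid arms.

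**Clinical judgement has value.** Haemoglobin down to 7.0 g/dL and platelets down to 50,000/mm³ are allowed at entry, and transient or TB-related values will occur. This stands. It is a reason to keep the investigator-reported endpoint and to require worsening from baseline in any count-based rule.

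**The table slips are editorial.** Agreed. The title of Table 3.2.18 is a copying error under a correct heading, the creatinine tables are likewise titled potassium, and the appendix says shells may be updated. The error does not show that haemoglobin will go unanalysed.

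**Conclusion.** The point holds as a gap in ascertainment that is cheap to close. The haematology part of the primary safety endpoint passes through two judgements by an investigator who knows the arm, and the planned laboratory outputs would not reveal their effect. The relatedness condition also leaves the endpoint without a background rate from Arm 1, although the stated objective is a comparison with the regimen without delpazolid.

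The only size that needs no assumption is 6.7 points per case per arm. The other figures rest on assumed risks and recording shares. The documents do not say how often a Grade 2 count would be left unrecorded or rated unrelated. A claim that the endpoint is biased for or against a particular dose would go further than they allow; the direction is unknown. The conclusion also relies on CTCAE 5.0 as the trial's adopted scale, since its numeric limits for counts are printed in neither document.

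**What to change.** Keep the protocol-defined endpoint unchanged. Making a count-derived rate part of it would drop the relatedness condition for three components and depart from Protocol 9.1.1.

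In SAP 5.1.1 and 13.2, pre-specify a supporting analysis in the safety population:
- **Rule:** any scheduled or unscheduled post-baseline count that reaches CTCAE 5.0 Grade 2 or higher and is at least one grade above baseline, for leukopenia, anaemia or thrombocytopenia. Print the numeric limits used.
- **Scope:** all five arms, irrespective of AE status and relatedness.
- **Display:** number and proportion with exact 95% CI by arm, next to the investigator-reported endpoint. The adverse event shells (appendix 3.4) contain no table for the primary safety endpoint itself, so one new shell can hold both.

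Unscheduled counts depend on the investigator too, so a version from scheduled visits alone would be a useful check. Add a leukocyte shell and correct the title of Table 3.2.18 to haemoglobin.

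The cost is one derivation, the shells and SAP wording; no visit, sample or aspect of treatment changes. The downside is that some transient or TB-related low values will count, by an amount the documents do not allow to be estimated. Intervals will be wide: 0 of 15 has an exact upper limit of 21.8%, and 3 of 15 runs from 4.3% to 48.1%.

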## 14.3 Additional immediately reportable events

The following events are notable events and need to be reported to the Sponsor within 24 hours of the site becoming aware of the event:

- Pregnancy while on study treatment,
- QTc prolongation meeting a stopping criterion
- any toxicity or condition that leads to a planned deviation from study medication
- any grade 4 event that is defined as probably or definitely related to study treatment by the investigator, and does not meet criteria for seriousness or other immediately reportable events

#### **14.4** Eliciting adverse event information

Patients will be instructed during informed consent to report occurrence of adverse events to the investigator, also between study visits and if not directly asked for.

Patients will be instructed to contact the investigator outside the schedule in case of a new complaint, or worsening of an existing complaint, that they feel is severe.

At every study visit, patients will be asked to describe their complaints, and report new occurrences.

Physical examination findings, weight, vital signs, ECG and laboratory information will be gathered as described by the study schedule of events. Additional investigations will be ordered by the investigator, if they are in the subject's best interest.

# 14.5 Assessment of Causality

The Investigator will review each AE and assess its relationship to study treatment based on all available information at the time of the completion of the CRF.

Each sign or symptom reported will be graded on a 5-point severity scale (see below). Additionally, the date and time of onset, relationship to the study medication, duration, action taken, and outcome (resolved, improved, unchanged, worse, fatal, or unknown (lost to follow-up) of each event will be noted.

Relationship	Description	Event Type (if Serious)	
Unrelated	There is no evidence of any causal relationship	Unrelated SAE	
Unlikely	There is little evidence to suggest there is a causal relationship (e.g. the event did not occur within a reasonable time after administration of the trial medication). There is another reasonable explanation for the event (e.g. the patient's clinical condition, other concomitant treatment).	Unrelated SAE	
Possible	There is some evidence to suggest a causal relationship (e.g. because the event occurs within a reasonable time after administration of the trial medication). However, the influence of other factors may have contributed to the event (e.g. the patient's clinical condition, other concomitant treatments).	SAR	
Probable	There is evidence to suggest a causal relationship and the influence of other factors is unlikely.	SAR	
Definitely	There is clear evidence to suggest a causal relationship and other possible contributing factors can be ruled out.	SAR	

The following definitions for rating attribution/causality will be applied:

Factors to be considered in judging relatedness include:

- The temporal sequence from drug administration.
- Recovery on discontinuation (de-challenge), recurrence on re-administration (rechallenge).
- Underlying, concomitant, intercurrent disease.
- Concomitant medication or treatment.
- Known response pattern for the classes of drug the participant is receiving
- Exposure to physical and/or mental stresses.
- The pharmacology and PK of the medication used.

